1. PURPOSE OF STUDY

The purpose of this study is to test the feasibility of a telehealth Dyadic Life Review (DLR), adapted from individual Life Review Therapy, with caregivers of older adults with advanced cancer, including those with Mild Cognitive Impairment (MCI). The study will enroll dyads of caregivers and older patients with advanced cancer and dyads of caregivers and patients with advanced cancer and Mild Cognitive Impairment (MCI). Life Review Therapy has only been delivered individually and there are no dyadic mental health interventions designed to target the mechanism of communal coping and reduce distress and emotional health outcomes in both older patients with advanced cancer and their caregivers. This innovative pilot study will gather data to test the feasibility of adapting Life Review Therapy to be delivered as a dyadic life review (DLR) and examine pre-post intervention changes in caregiver psychological distress.

1.1. Objective and Specific Aims (40 patient/caregiver dyads):

Objective: The research team will adapt and refine a dyadic life review intervention for older patients with advanced cancer, older patients with advanced cancer and MCI, and their caregivers. A mixed methods (i.e., integration of qualitative and quantitative data) approach will be used to gain understanding of the usability and feasibility of a telehealth DLR intervention with older adults with advanced cancer and their caregivers and examine effects on distress and emotional health in both the patient and caregiver.

1.2 Primary Aim:

1.2.1 To evaluate the feasibility of the dyadic life review intervention in older patients advanced cancer, with or without MCI, and their caregivers by determining consent rate, intervention adherence rate, and patient/caregiver acceptability. Hypothesis: We will achieve a dyad consent rate of 70%, dyad intervention adherence rate of 70%, and the intervention will be generally acceptable by dyads (determined from semi-structured interviews).

1.3 Secondary Aims:

1.3.1 To examine the pre-post change in the primary outcome of caregiver self-reported psychological distress, and secondary outcomes of caregiver loneliness, relationship satisfaction, and mental health outcomes, and changes in the associations between patient and caregiver distress.

1.4 Mixed Method Aim:

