4.2 STUDY INTERVENTIONS

DLR will consist of 8 sessions delivered by a trained licensed clinician (i.e, the PI or other trained clinician) via video-conferencing in weekly sessions of 60 minutes. Each session will facilitate a recall of each phase of life (Table 1). The patient and caregiver will each be asked structured questions to prompt reminiscence of memories from that phase of life. The DLR intervention guide attached to this protocol provides a framework of questions for each session, which follow the current standardized Life Review Handbook.²⁰ The guide acts as a framework, interventionist are able to use clinical judgment to prompt further or ask follow the patient and caregiver if pertinent events are being recalled outside of that time period. This will provide data to examine the feasibility of the DLR intervention and adapt and refine the intervention to the study's target population. Additionally, the patient and caregiver will be asked to recall if either the patient's or caregiver's recalled memory parallels the other's experiences (e.g. To Caregiver: "Does any aspects of [patient's] experience make you think of your own experiences around that time period?"). The fourth session will review recalled memories and focus on promoting communal coping in the present by drawing parallels of strength and resilience to managing MCI and cancer. The final session will review shared memories, from time periods the dyad was together, to enhance communal coping through connecting

shared memories. Each session will have flexibility for clinical judgement.

Table 1: Intervention Overview

Week	Session Life Period
1	Childhood
2	Adolescence
3	Young Adulthood (20-35 years)
4	Mid-Intervention review and dyadic processing
5	Mid-life (35-50 years)
6	Earlier later life (50-65 years)
7	Later life (65 years +)
8	Final review of shared memories and dyadic processing

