- Baseline: Following informed consent, patients and caregivers will undergo Time Point (TP) 1 measures. Patients will be provided a data-enabled tablet with HIPAA-compliant video-conferencing application and instructed on its use, along with tablet instructions. The study coordinator will assign each dyad a unique meeting ID number within the table instruction manual. This ID number will allow the dyad to log in to the video-conferencing application for each session. The study coordinator will train and support participating dyads on how to use the tablet and video-conferencing application. If patients and caregivers consent to have sessions and interviews recorded, this will be done through a HIPAA-compliant zoom software. If participating dyads do not have access to internet, a data plan will be provided for purpose of the study. No data will be stored on the tablet. At completion of the study, participants will return the tablets to the study coordinator. If tablets are lost or stolen, no PHI will be stored on the tablet, so this will not be accessible. The participants will contact the study coordinator with any concerns about the tablets. If a tablet is broken during the course of the study, another tablet will be provided.
- Intervention Period: The intervention period is 8 weeks; eight weekly 60 minute sessions will be delivered through video-conferencing. The sessions will be audio-recorded to ensure fidelity. Interventionist may use their clinical judgement to modify session lengths or shift session topics based on patient and caregiver expressed needs during sessions.
- Follow-up: Within 2 weeks of intervention completion (weeks 9-10), patients will be administered the UBACC to determine the patients maintained capacity to consent through the duration of the study; patients and caregivers will undergo TP 2.
- Patient and Caregiver measures will be performed by the PI or a trained study coordinator. TP1 and TP2 measures can be completed either in person or through videoconferencing. Study staff will score assessments and enter into a REDCap database.
- Semi-structured interviews: 80 separate patient and caregiver interviews (from 40 dyads) will be conducted by the PI or a trained study coordinator within 2 weeks after completion of the intervention. Interviews will be audio-recorded, in a private space, by telephone with the patient and caregiver separately.

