16. DATA ANALYSIS PLAN

16.1 Sample Size Considerations: In order to assess feasibility, using a reference of 0.5 for consent and adherence rate, 40 dyads would achieve 83% power using a one-tailed test at significance of 0.05. The quantitative data will be used to guide sample size calculations for a future randomized pilot. Therefore, a sample of 40 patient/caregiver dyads will support the assessment of feasibility of the telehealth DLR with older patients and caregivers and allow for thematic saturation through qualitative semi-structured interviews.

16.2. Analysis of Aims:

16.2.1 Primary aim: To evaluate the feasibility of enrolling and delivering the telehealth DLR intervention, we will calculate proportion of: 1) approached patient/caregiver dyads who enrolled (70%); 2) enrolled dyads who completed all 8 DLR sessions (70%); and 3) general acceptability of the DLR intervention by patients and caregivers. General acceptability will be examined through coding of transcribed semi-structured interviews from the 40 dyads (separate interviews for patients and caregivers; 40 patient interviews and 40 caregiver interviews). A sub-group analysis will examine any differences between older patients with only advanced cancer and their caregivers and older patients with both advanced cancer and MCI and their caregivers in enrollment, adherence, and acceptability.

16.2.2 Secondary and Exploratory Aims: To examine the pre-post change in caregiver psychological distress, we will utilize a regression analysis that will include the pre-measurement of caregiver distress as a covariate. We will also include gender and income as covariates in this model. A regression analysis will also be used to examine changes in the exploratory measures using the same covariates. A sub-group analysis will compare the difference in changes from pre to post intervention between dyads that include older patients with only advanced cancer and dyads with older patients with both advanced cancer and MCI.

16.2.3 Mixed Methods Aim:

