Qualitative Data Analysis: Semi-structured interviews will be audio-recorded and transcribed into MAXQDA software for coding and analysis. Abductive analysis will be used to code transcribed interviews and extract themes. Two independent coders will code the data until thematic saturation is achieved. Coding will be compared and discrepancies resolved through an iterative process and achieving consensus. Semi-structured interviews will gather information about the acceptability of the intervention, perceptions of the dyadic approach to the interventions, and evaluate patient and caregiver perceptions of communal coping. A sub-group coding analysis will be performed to examine any differences in responses between older patients with only advanced cancer and their caregivers and older patients with both advanced cancer and MCI and their caregivers.

Integration: Qualitative and quantitative data, including baseline and follow up measures and

transcribed semi-structured interviews, will be integrated to develop a more complete understanding of the feasibility of a telehealth DLR intervention in this unique population and to gain understanding of the patient and caregiver experiences and gather thick descriptions about barriers and facilitators for the intervention. The qualitative data can provide explanatory data for any changes in the quantitative measures from pre to post intervention for both patients and caregivers.

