
Interview Script for Patients/Caregivers:

Interviews will cover several broad topics; interviewers will probe participants' responses for more detail as needed.

The same questions will be asked of both patients and caregivers, who will be interviewed separately. Names will be used wherever possible in place of bracketed terms.

1. "What are some strengths you see in this type of intervention?"
 - a. "What did you like most about the intervention?"
2. "What are some limitations you see in the current intervention you were provided information about?"
 - b. "What did you dislike about the intervention?"
3. "How do you feel about the length of the total intervention?"
4. "How do you feel about the length of each session?"
5. "How suitable is this intervention give your current demands and daily responsibilities?"
6. "What, if any, are memories or experiences you feel you would not want to share with [caregiver/patient]?"
7. "What, if any, are some memories or experiences you feel are most important to share with your caregiver?"
8. "What were your impression of the first half of the intervention (weeks 1-4), how did you feel about sharing about your childhood, adolescents, and young adulthood?"
9. "What were your impression of the second half of the intervention (weeks 4-8), how did you feel about sharing about middle age and more recent memories and experiences?"
10. "What would you have changed about this dyadic life review intervention?"
11. How did this intervention help your relationship with your partner?
12. "How do you cope with this illness?"
 - a. "Have [repeat identified coping strategies] changed since doing this dyadic life review?"
 - b. "If so, how have they changed?"
13. "What does coping look like between you and your partner?"
 - a. "Can you give examples of what that looks like?"
14. "If you experienced loneliness or a sense of isolation before this, how did that change during the intervention?"
 - a. "If these experiences did change for you, what helped this to change?"
15. "If you're willing, what were some things you and [caregiver/patient] talked about on the way home from the session or the night after that session?"

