4b. [Patient] What did this memory [Caregiver] just share make you feel or think about?

5. If applicable to patient/caregiver:

For romantically involved dyads: Did you two meet during this time period? If so, tell me about this time and what you felt? What you thought about?

5a. [Caregiver] What did this memory [Patient] just share make you feel or think about?

For parent/adult child dyads: What was it like becoming a parent during this time?

5b. [Caregiver] What did this memory [Patient] just shared about becoming a parent make you feel or think about?

*Note: these questions from 5 can be shifted to whichever time period session the patient met their significant other caregiver, friend caregiver, or to the period they became a parent if it does not fall within this period.

Session 4: Dyadic Processing and Review of Session 1-3

Welcome and thank you for your time today. Today we will be focusing on reviewing what you have each shared up to this point. I will have some questions to help us get started with our conversation. There is no right or wrong response. You are free to move through memories as they come and I [the interventionist] may prompt for more detail or information as you recall these events.

[Direct questions to first patient then the caregiver, when possible use patient and caregivers' names to support building rapport through this process]

1. How are you feeling today?
2. Let's take a minute and recall some of the memories both [Patient] and [Caregiver] shared over the first three sessions.
 - 2a. [Patient] what has stood out to you up to this point about what [Caregiver] has shared thus far?
[Caregiver] what about you? What has stood out?
 - 2b. [Patient] Is there a memory you haven't shared so far that you are particularly proud to share with [Caregiver]?
[Caregiver] what about you? Is there a particular memory you have shared or still would like to share that you are particularly proud of?
3. [Patient] how would you describe your perception of [Caregiver] after recalling periods of your life together?
 - 3a. [Caregiver] how would you describe your perception of [Patient] after recalling these periods of life together?
4. We have talked about a large portion of your lives so far, share with me your overall feelings about these memories and periods of your life.
 - 4a. [Caregiver] What did what [Patient] just share make you feel or think about?

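### Interview question 11 presumes that the intervention helped the relationship; neutral wording would remove a risk of favourable bias on that theme

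*Combined protocol and SAP*

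**What the plan says.** The Interview Script for Patients/Caregivers, appended after Section 17, has 16 numbered questions, put in the same form to patients and caregivers in separate interviews. Question 11 reads "How did this intervention help your relationship with your partner".

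The plan uses these interviews in two ways.

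- **Acceptability.** The primary hypothesis in Section 1.2.1 includes that "the intervention will be generally acceptable by dyads (determined from semi-structured interviews"). The Data Analysis Plan, Section 16.2.1, adds that "General acceptability will be examined through coding of transcribed semi-structured interviews from the 40 dyads".
- **Explanation.** Section 1.4.1 assigns the interviews the task of accounting for change, or its absence, in the quantitative measures. The integration paragraph of Section 16.2.3 repeats this. Caregiver relationship satisfaction is a secondary outcome in Section 1.3.1. Section 8.1 lists three instruments for the relationship domain, given to both members of the dyad: the Unidimensional Relationship Closeness Scale, the DAS-7 and the DSQ.

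Section 16.2.3 names acceptability first among the interview topics ("Semi-structured interviews will gather information about the acceptability of the intervention"), followed by views on the dyadic approach and on communal coping.

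**The concern.** A question that asks how something helped leaves the respondent to volunteer that it did not help, or that it caused strain. Reducing relationship distress is a stated goal of DLR (Section 2.3). Section 9 lists emotional distress among the intervention's main risks and does not rule out negative outcomes. An unchanged or strained relationship is therefore a foreseeable experience, and the item on that subject should be able to record it.

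What is at stake is mainly the explanatory use of the interviews. If a dyad's relationship scores stay flat or worsen, a question that assumes improvement is poorly suited to finding out why.

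The setting adds some weight. Section 4.2 has DLR "delivered by a trained licensed clinician (i.e, the PI or other trained clinician"), and Section 8.2 says the interviews "will be conducted by the PI or a trained study coordinator within 2 weeks after completion of the intervention". The plan thus allows the same person to deliver the sessions and then ask how they helped, though it does not say how often this would happen.

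**Working it through.** **1. The plan's own figure.** The only calculation in the plan is 83% power (Section 16.1). Inputs: 40 dyads, reference rate 0.5 and one-tailed 0.05 from Section 16.1; target rate 0.7 from Section 1.2.1. With the normal approximation, power = Φ[(0.2 × √40 − 1.645 × √0.25) / √0.21] = Φ[(1.265 − 0.822) / 0.458] = Φ(0.966) = 0.833. The figure reproduces. It concerns consent and adherence only. The plan gives no numeric criterion for acceptability, so no bias in the interviews can be put on a numerical scale. The rest of the check compares wording.

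**2. Question 11 against the script's other items on effects or sensitive topics.**

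| Question | Topic | Is a direction assumed? |
|---|---|---|
| 6, 7 | Memories to withhold or to share | No; both allow for there being none |
| 12a, 12b | Change in coping | No; asks whether there was change, then how, if so |
| 14, 14a | Change in loneliness | No direction; the opening and the follow-up are both conditional |
| 11 | Effect on the relationship | Yes; improvement |

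Question 11 is the only item that fixes the direction of an intervention effect, so it departs from the script's own practice.

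**3. Does another item cover the same ground?** Question 13 asks what coping looks like between the two people, not whether DLR altered it. Question 12 concerns the respondent's coping and question 14 loneliness. Question 6 asks what the respondent would not want to share with the other person. Question 15 asks what the two talked about after a session. None asks what DLR did to the relationship.

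**4. Do the items bearing directly on acceptability lean the same way?** Questions 1 and 2 pair strengths with limitations and likes with dislikes. Questions 3 and 4 ask openly about length, question 5 about suitability, and questions 8 and 9 about impressions of each half. Question 10 asks what the respondent would change and question 16 invites any other feedback. This set is balanced.

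**5. Exposure.** 40 dyads × 2 separate interviews = 80 interviews, each with question 11 as one of 16 numbered items. This is how often the question would be put, not how far answers would move.

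**The case against.** The strongest reply is that one item in 16 cannot carry much. Question 11 fits the dyadic-approach and communal-coping topics more naturally than acceptability. Respondents can reject the premise, the script lets interviewers probe, and the two members of a dyad are interviewed apart so that each can speak freely. Two coders work independently and resolve differences by consensus (Section 16.2.3), and they code the answer, not the question. The relationship scales are completed separately and do not depend on question 11. All of this stands. It limits the reach of the point but does not make the question neutral.

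Four stronger readings are tempting, and the documents do not support them.

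- **That every dyad will be coded as having benefited, or that the acceptability result is pushed upward.** Step 4 and the safeguards just listed argue against this. The absence of a control arm does not change it, since acceptability here is a non-comparative qualitative judgement.
- **That *partner* presumes a spouse and so biases answers.** The intervention guide does expect other pairs ("For parent/adult child dyads: What was it like becoming a parent during this time"), and Section 5.3 admits friends and family members. But Section 8.1, on the interviews, uses the word for either member of the dyad. It is ambiguous at most, and ambiguity about who is meant does not favour DLR.
- **That question 15 rests on travel that never happens.** It mentions what was "talked about on the way home from the session", but offers later that night as an alternative. Section 3.3 also lets participants join from a private place other than home. This is untidy, not biasing.
- **That the general criticism items already deal with the problem.** They invite criticism of the intervention as a whole and do not ask about its effect on the relationship.

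**Conclusion.** The point holds in a limited form. Question 11 is a leading question, it alone addresses DLR's effect on the relationship, and it creates a risk of favourable bias on that theme. The consequence is clearest for the mixed-methods aim, where the transcripts must explain null or adverse change as well as improvement. The transcripts also feed the acceptability component of the primary aim, but a shift in that result is not shown. The direction of any bias is favourable to DLR; its size cannot be derived from the documents.

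This rests on two assumptions: that interviewers put the question roughly as written, and that some respondents will go along with its premise unless invited to do otherwise. The documents neither confirm nor contradict either one. Consent rate, adherence rate, the power calculation and the questionnaire scores are unaffected. The point is a free improvement.

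**What to change.** Reword question 11 to: *How, if at all, has this intervention affected your relationship with [caregiver/patient], for better or worse?* The placeholder is already used elsewhere in the script.

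Three optional edits would improve clarity; they are not bias corrections:

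- use the same placeholder in question 7, which says *your caregiver* although caregivers are asked it too;
- use it in question 13 in place of *partner*;
- in question 15, replace the journey home with *after the session ended*.

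The cost is one script line, or four with the optional edits. Visits, interview number, sample size and analysis stay as they are.
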